6.2. Secondary Endpoint(s)

6.2.1. Arm span to height/length difference

6.2.1.1. Main Analysis

- Estimand strategy: Hypothetical ([Section 2.1.1](#)).
- Analysis set: FAS ([Section 4](#)).
- Analysis methodology: Change from baseline for Arm span to height/length difference will be analyzed MMRM including data from Months 3, 6, 9, and 12 with gender as a covariate, subject (and/or time) as a random effect and an unstructured covariance matrix ([Section 5.2.1](#)).
- Intercurrent events and missing data: Data after study drug discontinuation and rescue will be excluded; intermediate missing values will not be imputed.
- The sample size, mean, standard deviation, median, minimum, and maximum at the baseline and postbaseline visits for observed standing height and change from baseline will be presented for each treatment arm.

The least-squares (LS) means, the 95% confidence interval for the LS means, the difference between the LS means for each pair of treatment groups, and the corresponding 95% confidence interval will be presented for change from baseline in standing height for all postbaseline visits.

6.2.1.2. Sensitivity/Supplementary Analysis

The main analysis will be repeated by using the per-protocol analysis set (PPAS) as defined in [Section 6.2.1.1](#).

6.2.2. Sitting height/standing height ratio

- Analysis set: FAS ([Section 4](#)).
- Intercurrent events and missing data: Data after study drug discontinuation and rescue will be excluded; intermediate missing values will not be imputed.
- The sample size, mean, standard deviation, median, minimum, and maximum at the baseline and postbaseline visits for observed sitting height/standing height ratio and change from baseline will be presented for each treatment arm.

6.2.3. Knee height:lower segment ratio

The analysis set, analysis methodology and intercurrent events and missing data are the same as [Section 6.2.2](#).

6.2.4. Occipito-frontal circumference

The analysis set, analysis methodology and intercurrent events and missing data are the same as [Section 6.2.2](#).

6.2.5. Ratio of occipito-frontal distance to occipito-mid-face measurements

The analysis set, analysis methodology and intercurrent events and missing data are the same as [Section 6.2.2](#).

6.2.6. Z-score of the above proportionality and skull morphology where achondroplasia reference datasets exist (occipito-frontal circumference, arm span, sitting height)

The analysis set, analysis methodology and intercurrent events and missing data are the same as [Section 6.2.2](#).

6.2.7. Fixed flexion angles at elbow

The analysis set, analysis methodology and intercurrent events and missing data are the same as [Section 6.2.2](#).

6.2.8. Polysomnography parameters in those with pre-existing sleep-disordered breathing at the time of enrolment

The analysis set, analysis methodology and intercurrent events and missing data are the same as [Section 6.2.2](#).

6.2.9. BMI

The analysis set, analysis methodology and intercurrent events and missing data are the same as [Section 6.2.2](#).

6.2.10. Waist:chest circumference ratio

The analysis set, analysis methodology and intercurrent events and missing data are the same as [Section 6.2.2](#)

6.2.11. CHAQ component and index scores; QoLISSY Brief total score

The analysis set, analysis methodology and intercurrent events and missing data are the same as [Section 6.2.2](#).

6.2.12. Population PK characterization in children aged ≥ 2 to <11 years old with achondroplasia.

The analysis set for this endpoint will be the PK concentration set ([Section 4](#)); nonlinear mixed effect modeling will be performed to evaluate pharmacokinetic parameters. Additional details on the population PK modeling will be described in the population modeling analysis plan.

6.2.13. Rate of anti-drug antibodies

- Analysis set: FAS

Response rates of the development of anti-recifercept antibodies (ADA) and NAb. The percentage of subjects with positive ADA and NAb will be summarized by dose and cohort. For subjects with positive ADA or NAb, the magnitude (titer), time of onset and duration of ADA/NAb response will also be described, if data permit. The impact of ADA and NAb on PK and/or safety may also be assessed, if data permit. This may include:

- Spaghetti plots of individual intact and total recifercept concentration time profile, grouped by ADA/NAb status, produced separately by cohort.
- Table summaries of intact and total recifercept concentrations at visit and time by ADA and NAb status by cohort.

CCI

6.4. Subset Analyses

Not applicable.

6.5. Baseline and Other Summaries and Analyses

6.5.1. Baseline Summaries

Demographics and baseline disease characteristics defined in [Section 3.4](#) will be summarized by treatment group according to Pfizer standards.

6.5.2. Study Conduct and Participant Disposition

Subjects evaluation, disposition, discontinuation will be summarized according to Pfizer standards. .

6.5.3. Study Treatment Exposure

The exposure to study drug will be summarized by total number of applications, the total number of days of dosing, the number and the proportion of participants who are compliant with the dosing regimen.

6.5.4. Concomitant Medications and Nondrug Treatments

Prior drug and non-drug treatment, concomitant drug and non-drug treatment will be summarized according to Pfizer standard.

6.5.5. Tanner Stage

Tanner stage and the change from baseline will be summarized at each visit by dose and gender.

6.6. Safety Summaries and Analyses

All safety analyses will be performed on the safety population and summarized in accordance with Pfizer Data Standards.

All clinical AEs, SAEs, TEAEs, withdrawal due to AEs, ECGs, vital signs and safety laboratory data will be reviewed and summarized on an ongoing basis during the study to evaluate the safety of participants.

Safety data will be summarized descriptively through appropriate data tabulations, descriptive statistics, categorical summaries, and graphical presentations, where appropriate. Categorical outcomes (eg, AEs) will be summarized by subject counts and percentage. Continuous outcome (eg, blood pressure, pulse rate, etc.) will be summarized using N, mean, median, standard deviation, etc. Change from baseline (CFB) in laboratory data, and vital signs will also be summarized. Participant listings will be produced for the safety endpoints accordingly.

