The study is a phase 2, randomized, dose-finding study of safety, tolerability, pharmacokinetics, and efficacy. Approximately 63 participants will be randomized to one of three doses (1mg/kg once weekly, 2 mg/kg twice-weekly, 1.5 mg/kg once-daily) for 12 months. Participants will be children diagnosed with achondroplasia aged ≥ 3 months to < 11 years; enrollment will progress in an age and dose staggered manner (descending age and ascending dose). Progression to the next enrollment block will be after review of safety and PK data, including review by an external data monitoring committee (eDMC) if safety signals are identified. In order to minimize bias in measurement of the primary efficacy endpoint (height), the anthropometrist will be blinded to dose assignment. There will be no additional blinding.

An interim analysis will be performed when approximately 45 participants (up to 15 participants per dose) aged ≥ 2 to < 11 years have received 6 months of treatment with reciferecept.

All participants who complete the study and in the opinion of the investigator, continue to have a positive risk: benefit profile, will be offered to enroll into an open-label extension (OLE) study. Participants will continue to receive reciferecept at the dose previously received in this phase 2 study or at the therapeutic dose once this is identified.

PK Study Cohort:

At selected sites only, an additional PK cohort has been added to evaluate the PK of two reciferecept formulations (process 1c and process 2). A total of 12 children with achondroplasia aged 2- < 11 years will be enrolled in the PK cohort (6 in each treatment sequence). Each participant will receive 2 treatments (3 mg/kg Phase 2 formulation [process 1c] and 3 mg/kg Phase 3 formulation [process 2]) in a randomized manner according to one of two sequences.

Number of Participants

Approximately 54 participants aged 2-10 inclusive at the time of informed consent will be randomly assigned to study intervention enrolled such that approximately 45 evaluable participants complete the study. In addition, 9 participants aged ≥ 3 months - 2y at the time of informed consent will be enrolled in **CCI** cohort.

PK Study Cohort:

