- g. Participants must have dosing performed at site with clinical observation for a minimum of 4 hours post-dose for first 5 doses (**Once daily dosing; Days 1-5, Twice-weekly dosing; Days 1, 4, 8, 11, 15, Once-weekly dosing; Days 1, 8, 15, 22, 29**). Staff administering the dose should be trained in management of acute hypersensitivity with access to appropriate facilities to treat such events. Following appropriate training, dosing will then be performed at home. First dose at home to be observed by home nursing. Dosing may be performed in the clinic at any time if investigator determines that home dosing is not feasible or appropriate.
- h. Sleep study to be performed only in participants with a documented diagnosis of sleep-disordered breathing prior to enrollment. Baseline PSG data can be within 6 months prior to enrollment. Final PSG to be ±1 months of M12 visit.
- i. [REDACTED]
- j. Samples to be drawn pre-dose unless otherwise specified.
- k. Day 61 sample to be taken pre-dose and between 20 – 28 h post-dose for participants receiving once- or twice-weekly dosing (2 samples in total). Once-daily dosing participants will have only the pre-dose sample (1 sample in total).
- l. Day 91 sample to be taken pre-dose and between 40-56h post-dose for participants receiving once- or twice-weekly dosing (2 samples in total). Once-daily dosing participants will have only the pre-dose sample (1 sample in total).

- m. Prep-D1.5 can be collected at any blood draw during the study, prep B1.5 to be collected at specified time points.
- n. M4 & M5 are telephone contact only and for dispensing medication using the Interactive Response Technology (IRT) system, except Japan safety assessment (at least but not limited to: AE/SAE, concomitant treatment) should be confirmed via physical site visit or telehealth before dispensing. M7, M8, M10 & M11 are for dispensing medication using the IRT system. No on-site visit is scheduled for M7, M8, M10 & M11, except Japan safety assessment (at least but not limited to: AE/SAE, concomitant treatment) should be confirmed via physical site visit or telehealth before dispensing. Drug may be shipped to the participants home after dispensing. Site personnel can register the visits anywhere in the SoA window and schedule pick up and delivery. Site personnel should not register multiple visits at once, except under special circumstances, eg, the patient is traveling out of the country for a long duration.

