2.2.1. Clinical Overview

As of September 2021, a total of 32 participants were enrolled from 2 to 10 years old. 14 participants were randomized to 1 mg/kg once weekly (QW) arm and 15 participants were randomized to 2 mg/kg twice weekly (BIW) dosing arm and 3 participants were randomized to 1.5 mg/kg daily (QD). A total of 36 treatment related AEs were reported from 13 out of 32 participants; 3 at low dose, 8 at medium dose and 2 at high dose. The most frequently reported AEs were ISRs such as redness/rash/erythema/pruritis at the injection site. All AEs were mild or moderate in severity and there were no serious adverse events. There were no other clinically significant laboratory abnormalities or physical examination/vital sign changes. Following, administration of study drug, observed serum recifercept concentrations at all three doses were in the range of the predicted exposures in 2 to <10 year old children with achondroplasia using the population PK (PopPK) model.

In the recifercept Phase 1 study (C4181002), healthy participants were administered single (n=30) and multiple (n=24) SC doses of recifercept. In addition, 18 participants received placebo in the study. The dose-range studied in single ascending dose (SAD) part of the study was 0.3 – 20 mg/kg and in the multiple ascending dose (MAD) part was 1 mg/kg and 3 mg/kg twice weekly and 3 and 10 mg/kg once weekly for four weeks. Signs and symptoms of an injection site/infusion site reaction, including erythema, swelling, pain, inflammation, and pruritis, were the most frequently reported adverse events in the SAD and MAD part of

the study. There were no clinically significant changes in laboratory tests, vital signs or ECG. No systemic allergic reactions or serious adverse events occurred during the study.

In the SAD portion of the study, all participants were ADA negative (ADA-) prior to treatment with reciferecept. A confirmed ADA positive (ADA+) response was observed in 8 participants receiving reciferecept and 1 placebo participant at the end of the study (Day 29). In the MAD portion of the study, 2 participants were ADA+ prior to treatment with reciferecept. The majority of the participants who received multiple doses of reciferecept were ADA+ (21/24) and 2 placebo participants during the observation period.

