4. STUDY DESIGN

4.1. Overall Design

This is a phase 2 randomized, 3 arm (3 active doses of Recifercept), parallel group dose- finding study of safety, tolerability, PK and efficacy.

The study will enroll approximately 54 children with achondroplasia aged 2-10 years (inclusive) who will be enrolled and randomized to receive one of three doses of reciferecept (1 mg/kg once-weekly, 2 mg/kg twice-weekly or 1.5 mg/kg once-daily, n=18 per dose) such that approximately 45 participants are evaluable (up to 15 participants per dose). Additionally, **CCI** cohort of approximately 9 children with achondroplasia, ages 3 months to 2 years, will be enrolled later in the study (n=3 per dose). All 63 participants in this part of the study will receive reciferecept for 12 months.

PK Study Cohort:

At selected sites only, an additional PK cohort has been added to evaluate the PK of two reciferecept formulations. A total of 12 children with achondroplasia aged 2- < 11 years will be enrolled in the PK cohort (6 in each treatment sequence). Each participant will receive 2 treatments (3 mg/kg Phase 2 formulation [process 1c] and 3 mg/kg Phase 3 formulation [process 2]) in a randomized manner according to one of two sequences as outlined in [Table 1](#) below. Dose of the cohort could be changed due to emerging safety and efficacy data in the study.

PK samples collected following each dose will be analyzed to evaluate the exposures of two formulations.

Table 1. Treatment Sequence

Sequence	Period 1	Period 2
1 (n = 6)	Phase 2 study (process 1c) Formulation	Phase 3 study (process 2) Formulation
2 (n = 6)	Phase 3 study (process 2) Formulation	Phase 2 study (process 1c) Formulation

All participants who complete the study and in the opinion of the investigator, continue to have a positive risk: benefit profile, will be offered to enroll into an open-label extension (OLE) study. Participants will continue to receive recifercept at the dose previously received in this phase 2 study or at the therapeutic dose once this is identified.

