8.3.8. Adverse Events of Special Interest

Injection site reactions will be considered an adverse event of special interest (AESI). Injection site reactions may include but are not limited to erythema, induration, ecchymosis, pain and pruritis. The size and severity of these symptoms or reactions will be assessed and documented. The following details will be collected:

- Date of onset and resolution of the ISR;
- Presence of the following features on a mild/moderate/severe grading scale:
 - Erythema;
 - Induration;
 - Pain;
 - Swelling;
 - Pruritis.
- Did the ISR lead to any missed or delayed doses?
- Did the ISR lead to withdrawal of the participant from the study?

All AESIs must be reported as an AE or SAE following the procedures described in [Section 8.3.1](#) through [Section 8.3.4](#). An AESI is to be recorded as an AE or SAE on the CRF. In addition, an AESI that is also an SAE must be reported using the CT SAE Report Form.

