10.10. Appendix 10: Subcutaneous Dosing Instructions

SUBCUTANEOUS DOSING INSTRUCTIONS

GENERAL INSTRUCTIONS

- Allow prepared syringes with the medication to reach room temperature for 15 minutes prior to administration (they should not be cold to touch);
- Never reuse needles or syringes;
- Dispose of all used materials in the appropriate sharps container and return used vials into the cartons to be checked by a study monitor.

Gather your supplies:

- Alcohol pads;
- Prepared syringe with medication;
- Puncture resistant sharps container.

[figure not shown]
Choose one of the recommended injection sites described below:

The injection(s) should be given when participant is sitting or lying down into the **abdomen or outer thighs**. **The back of the arms may be used as an alternative injection site (Figure 2).**

Do not inject into areas where the skin is tender, bruised, red, or hard. Avoid areas with scars, moles and avoid the area 1 inch from the naval.

- Injections should start in either the abdomen or outer thighs at number one and proceed in a clockwise manner from site number 1 through to number 4.
- If injections are given in the back of the arms, alternate between the left and right arms.
- For each injection given (including if two injections are needed for one dose), a new injection site must be chosen. Inject at least 2 inches from the previous site.

[figure not shown]
Figure 2. Injection Site Rotation

Preparing the subcutaneous injection site and injecting Recifercept

[figure not shown]
1. Wash hands thoroughly with soap and water prior to any injections.
2. Choose the site from Figure 2 and clean the site where Recifercept is to be injected with a new alcohol swab, using a circular motion, starting from the inside and working to the outside of the chosen injection site. Allow the area to dry thoroughly, do not blow the area dry. DO NOT touch this area again before giving the injection.
3. Using the thumb and forefinger, lift up a fold of skin with one hand (Figure 3).

Figure 3. Technique for Holding Skin Prior to Injection

[figure not shown]
1. With the other hand, hold the syringe like a pencil with the bevel up. With a quick, short motion, push the needle into the skin at an angle of 45° (Figure 4).

Figure 4. Injection Angle

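### The SAP ties no exposure denominator to injection-site reactions, so the percentage of children affected cannot show how much of a difference between regimens reflects injection frequency

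*SAP*

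**What the plan says.** Safety and tolerability of the doses and regimens is a primary objective, measured by how often AEs and SAEs occur and how severe they are (SAP 2.1 and 3.1). The regimens differ in amount and in frequency. Protocol 1.1: "Approximately 63 participants will be randomized to one of three doses (1mg/kg once weekly, 2 mg/kg twice-weekly, 1.5 mg/kg once-daily) for 12 months".

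Protocol 8.3.8 singles out one event type: "Injection site reactions will be considered an adverse event of special interest (AESI". Protocol 2.2.1 reports that these reactions were also the most frequent AEs as of September 2021.

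On analysis, SAP 6.6 states: "Categorical outcomes (eg, AEs) will be summarized by subject counts and percentage". SAP 6.6.1 adds one sentence that refers AE reporting to the sponsor's standards, which are not among the documents. The SAP text describes no analysis specific to injection-site reactions. SAP 6.5.3 counts exposure separately: "The exposure to study drug will be summarized by total number of applications, the total number of days of dosing". Nothing links that count to AEs.

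Protocol 6.6.1 allows dose levels to be changed after a benefit-risk evaluation at the interim. SAP 7.1 gives the interim a safety purpose, but SAP 7.2 describes only the two growth analyses.

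**The concern.** A child on daily dosing has about seven times as many occasions for an injection-site reaction as a child on weekly dosing. The chance of at least one reaction can therefore rise across the arms even if a single injection is no riskier in one arm than in another. A reader of the planned table could not tell that situation from one in which each injection is riskier at the higher dose level. The two would mean different things for dose finding.

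For AEs that injections do not trigger, injection count is irrelevant. There the question is follow-up time. Enrollment ascends by dose (Protocol 4.1), so at the interim the later-opened high dose may have been observed for less time per child, and a crude percentage would then understate it.

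**Working it through.** **Inputs.** The dosing days in the schedule of activities (Protocol 1.3) confirm the frequencies: "Once daily dosing; Days 1-5, Twice-weekly dosing; Days 1, 4, 8, 11, 15, Once-weekly dosing; Days 1, 8, 15, 22, 29". Duration is 12 months. Planned size at ages 2-10 is 18 per arm (Protocol 4.1: "1.5 mg/kg once-daily, n=18 per dose"). The documents give no risk per injection, so p is an assumption shown over a range.

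**The plan's own figures.** As of September 2021 the children with treatment-related AEs were "3 at low dose, 8 at medium dose and 2 at high dose": 3 + 8 + 2 = 13, out of 14 + 15 + 3 = 32. These totals agree with Protocol 2.2.1.

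**Injections per year.** Weekly: 365/7 = 52.1. Twice weekly: 2 × 365/7 = 104.3. Daily: 365. These are minimum counts, because Protocol Appendix 10 provides for a dose that takes more than one injection ("including if two injections are needed for one dose").

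**Percentage with at least one reaction.** With equal, independent risk the formula is 1 − (1 − p)^n, with n = 52, 104 and 365. To let reactions cluster within children, use a beta-binomial with mean p and within-child correlation r: 1 − B(a, b + n)/B(a, b), where a = p(1/r − 1) and b = (1 − p)(1/r − 1).

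| Assumption | Weekly | Twice weekly | Daily |
|---|---|---|---|
| p = 0.1%, independent | 5.1% | 9.9% | 30.6% |
| p = 0.5%, independent | 22.9% | 40.6% | 84.0% |
| p = 1%, independent | 40.7% | 64.8% | 97.4% |
| p = 10%, independent | 99.6% | 100.0% | 100.0% |
| mean p = 0.5%, r = 0.01 | 19.0% | 30.0% | 53.6% |
| mean p = 0.5%, r = 0.05 | 11.9% | 16.5% | 25.0% |
| mean p = 0.5%, r = 0.5 | 2.2% | 2.6% | 3.2% |

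At p = 0.5% with independence, about 4.1, 7.3 and 15.1 of 18 children per arm would be affected. The rate would be 0.5 per 100 injections in every arm, by construction.

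**AEs that follow calendar time.** At an assumed one event per year, 1 − exp(−1) = 63.2% of children are affected after 12 months in every arm, so there is no gradient. After 6 months the figure is 1 − exp(−0.5) = 39.3%. A gap arises only if arms are compared at different follow-up.

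**Unequal follow-up and reactions.** A daily arm seen for 6 months (182 injections) would show 1 − 0.995^182 = 59.8% at p = 0.5%, against 84.0% at 12 months. Six against twelve months is an illustration; the documents do not give the actual spread of follow-up at the interim.

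**The case against.** The strongest reply is that the percentage affected is the right statistic for the stated objective. Injection frequency is part of each regimen, and a child dosed daily does carry the cumulative burden. This stands: the percentage is not biased as a description of a regimen. It just does not attribute the cause.

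Safety is also descriptive, no statistical comparison between doses is planned in the protocol (9.2), and block progression depends on named event counts (Protocol 6.6.1). This limits the consequence. It does not remove it, because benefit-risk at the interim will still be judged from descriptive tables.

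Four stronger readings are tempting, and the documents do not support them:

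- A reader might infer that AEs will be tabulated as percentages and in no other way. That cannot be confirmed. SAP 6.6.1 defers to sponsor standards that we cannot see, severity is part of the endpoint, and listings are planned. A crude rate could be built from the SAP 6.5.3 counts.
- A reader might infer that all AEs will show a gradient driven by injections. Over an equal 12 months they would not, as the calendar-time check shows.
- A reader might take the September 2021 figures (21%, 53% and 67%) as the gradient in action. They cover treatment-related AEs in general, exposure at that cut-off is not given, and the exact 95% intervals are 5-51%, 27-79% and 9-99%.
- A reader might expect a rate per injection to isolate the effect of drug amount. It cannot: weekly amounts are 1, 2 × 2 = 4 and 7 × 1.5 = 10.5 mg/kg, so amount and frequency rise together.

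**Conclusion.** The point holds in a limited form. The SAP text names a per-child AE statistic and no exposure-based rate, in a trial whose arms differ about sevenfold in injections and whose event of special interest is a reaction to injection. How far the percentage would rise from frequency alone depends on assumptions that the documents cannot settle. At 0.5% per injection it is 23%, 41% and 84% under independence, and about 12%, 17% and 25% with a within-child correlation of 0.05. It is close to flat with strong clustering, or when nearly every child reacts. The planned table cannot tell the reader which of these applies.

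For AEs not triggered by injections the concern is only unequal follow-up. That arises chiefly at the interim, and to a lesser degree at the end if discontinuation differs between arms. This is a gap in interpretation that is cheap to close. It is not an error in the percentage itself.

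**What to change.** Keep the percentage table. In SAP 6.6.1 add:

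- Injection-site reactions by dose as events per 100 injections. Take the denominator from SAP 6.5.3 and the dosing diary, and count injections, since one dose may take two. Use intervals that allow for repeated events within a child, such as negative binomial or robust variance.
- A stated rule for counting reactions that overlap under daily dosing. Protocol 8.3.8 records onset and resolution dates but does not say how a reaction is assigned to an injection. Overlapping reactions merged into one would lower the daily arm's rate.
- AEs by dose per participant-year. At the interim, use participant-years or restrict every child to the first 6 months.
- A sentence saying that these rates adjust for injection count and follow-up but do not isolate the effect of drug amount.

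The cost is two extra descriptive tables. Protocol 6.4 already has each dose recorded with its date, time, site and volume, so conduct and sample size do not change.
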